Pre-existing conditions (present at the time of signing of informed consent) are considered concurrent medical conditions and should NOT be recorded as PTEs or AEs. Baseline evaluations (e.g., laboratory tests, ECG, X-rays) should NOT be recorded as PTEs unless related to study procedures. However, any abnormal finding related to study procedures (e.g., bruise after blood draw) should be recorded as a PTE. If the subject experiences a worsening or complication of a concurrent condition, the worsening or complication should be recorded appropriately as a PTE (worsening or complication occurs before start of study drug) or an AE (worsening or complication occurs after start of study drug). Investigators or sub-investigator should ensure that the event term recorded captures the change in the condition from baseline (e.g., “worsening of hypertension”).

If a subject has a pre-existing episodic condition (e.g., asthma, epilepsy) any occurrence of an episode should only be captured as a PTE/AE if the episodes become more frequent, serious or severe in nature. If a subject has a degenerative concurrent condition (e.g., cataracts, rheumatoid arthritis), worsening of the condition should only be captured as a PTE/AE if occurring to a greater extent to that which would be expected. The investigator or sub-investigator should ensure that the AE term recorded captures the change in the condition (e.g., “worsening of...”).

Worsening of PTEs or AEs:

If the subject experiences a worsening or complication of a PTE after starting administration of the study drug, the worsening or complication should be recorded appropriately as an AE. The investigator or sub-investigator should ensure that the AE term recorded captures the change in the condition (e.g., “worsening of...”).

If the subject experiences a worsening or complication of an AE after any change in study drug, the worsening or complication should be recorded as a new AE. The investigator or sub-investigator should ensure that the AE term recorded captures the change in the condition (e.g., “worsening of...”).

Changes in intensity of AEs /Serious PTEs:

If the subject experiences changes in intensity of an AE/serious PTE, the event should be captured once with the maximum intensity recorded.

Preplanned surgeries or procedures:

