- Study Day: The day before the start of the study drug administration will be defined as Day -1 and the day of the start of the study drug administration will be defined as Day 1.
- Follow-up Day for Treatment Period I: The day after the last administration of the study drug for Treatment Period I will be defined as Follow-up Day 1 for Treatment Period I.
- Study Day for Treatment Period II: The day before the start of the study drug administration for Treatment Period II will be defined as Day -1 for Treatment Period II and the day of the start of the study drug administration for Treatment Period II will be defined as Day 1 for Treatment Period II.
- Study Day for SYR-472 25 mg tablet: The day before the start of SYR-472 25 mg tablet will be defined as Day -1 for SYR-472 25 mg tablet and the day of the start of SYR-472 25 mg tablet will be defined as Day 1 for SYR-472 25 mg tablet.
- Follow-up Day for SYR-472 25 mg tablet: The day after the last administration of SYR-472 25 mg tablet will be defined as Follow-up Day 1 for SYR-472 25 mg tablet.
- Treatment groups: SYR-472 25 mg group (subjects who received SYR-472 25 mg in both Treatment Periods I and II), placebo group (subjects who received placebo in Treatment Period I and SYR-472 25 mg in Treatment Period II).

In this statistical analysis plan (hereinafter referred to as SAP), the treatment groups will be presented as the SYR-472 25 mg/SYR-472 25 mg group and the placebo/SYR-472 25 mg group.

- Summary statistics: number of subjects, mean, standard deviation, maximum, minimum, and quartiles
- Reason for not being treated with the study drug for Treatment Period II: If the subject is “Not treated” with the study drug for Treatment Period II, the reason why the administration of study drug was discontinued will be analyzed as the reason for not being treated with the study drug for Treatment Period II.
- Treatment-emergent adverse event (TEAE): An adverse event whose date of onset occurs on or after the start of the study drug administration. Since there is a possibility that the evaluation result of an adverse event may differ before and after the start of the study drug administration for Treatment Period II, the evaluation result of adverse event to be used for analysis will be defined according to the rules below:

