 - TEAEs that occur before the start of the study drug for Treatment Period II: The analysis will be performed based on the evaluation result entered in the CRF under “Pretreatment Event/Adverse Event (Period 1).”
 - TEAEs that occur after the start of SYR-472 25 mg tablet: The analysis will be performed based on the evaluation results entered in the CRFs under “Pretreatment Event/Adverse Event (Period 1)” and “Pretreatment Event/Adverse Event (Period 2 and thereafter).” If the

evaluation results differ between “Pretreatment Event/Adverse Event (Period 1)” and “Pretreatment Event/Adverse Event (Period 2 and thereafter),” the evaluation result of “Pretreatment Event/Adverse Event (Period 2 and thereafter)” will be preferentially used.

- Time of onset: In the analysis of TEAEs that occur before the start of the study drug for Treatment Period II, the time of onset will be calculated by defining the day of the start of the study drug administration as day 1. In the analysis of TEAEs that occur after the start of SYR-472 25 mg tablet, it will be calculated by defining the day of the start of SYR-472 25 mg tablet as day 1.
- Number of days from the immediate study drug administration: To be calculated by defining the day of the immediate study drug administration as Day 1. If the study drug administration and TEAE occur on the same day, the number of days from the immediate study drug administration will be defined as 1 day.
- Complications of hepatobiliary disorders: Concurrent medical conditions summarized as hepatobiliary disorders by SOC.
- MAV: An abbreviation for markedly abnormal value.
- Overall hypoglycemia: Hypoglycemia reported as “Yes” for hypoglycemic symptoms and asymptomatic hypoglycemia.
- Asymptomatic hypoglycemia: Hypoglycemia with an evaluable self-monitoring blood glucose value (i.e., non-missing and determined to be eligible based on “Handling Rules for Analysis Data”) and a measured concentration of ≤ 70 mg/dL but determined to be not accompanied by symptoms of hypoglycemia at the measurement of that blood glucose value. The presence or absence of asymptomatic hypoglycemia will be determined for each blood glucose value measured.

HANDLING OF TIME WINDOW

For each test, observation, and evaluation items, evaluable data (i.e., non-missing data and data determined to be eligible based on “Handling Rules for Analysis Data”) will be handled according to the following rules.

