3 SAFETY ANALYSIS

3.1 Treatment-Emergent Adverse Event

3.1.1 Overview of Treatment-Emergent Adverse Events

Analysis set:	Safety analysis set	
Analysis variables:	TEAEs that occur before the start of the study drug for Treatment Period II	
	TEAEs that occur after the start of SYR-472 25 mg tablet	
Categories:	Causality [Related, Not related] Intensity [Mild, Moderate, Severe]	
Analysis methodology:	
The following summaries will be provided for the above analysis variables by treatment group.
 
In the analysis of TEAEs occurring after the start of SYR-472 25 mg tablet, subjects who received SYR-472 25 mg tablet in the safety analysis set will be included in the analyses and the summaries in the consolidated treatment groups will be also provided.
	
	
(1) Overview of TEAEs
 
 1) All TEAEs (number of events, number and percentage of subjects) 2) Causal relationship between all TEAEs and study drug (number of events, number and percentage of subjects) 3) Intensity of all TEAEs (number of events, number and percentage of subjects) 4) TEAEs leading to study drug discontinuation (number of events, number and percentage of subjects) 5) Serious TEAEs (number of events, number and percentage of subjects) 6) Causal relationship between serious TEAEs and study drug (number of events, number and percentage of subjects) 7) Serious TEAEs leading to study drug discontinuation (number of events, number and percentage of subjects) 8) TEAEs leading to death (number of events, number and percentage of subjects) 	
	
TEAEs will be counted according to the rules below:
 
[Number of subjects]
 
 • In the case of “summaries by causality” 
A subject with occurrences of TEAE in both categories (i.e.,
	

“Related” and “Not related”) will be counted once in the “Related” category.

- In the case of “summaries by intensity”

A subject with multiple occurrences of TEAE will be counted once for the TEAE with the maximum intensity.

- In the case of summaries other than the above

A subject with multiple occurrences of TEAE will be counted only once.

[Number of events]

For each summary, the total number of events will be calculated.

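### An AE that began on placebo and is re-evaluated on SYR-472, without being entered as a new AE, has its later evaluation used in no SAP TEAE table; the same record in the SYR-472/SYR-472 group is analysed with it

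*SAP*

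**What the plan says.** **SAP, definition of terms.** A TEAE is "An adverse event whose date of onset occurs on or after the start of the study drug administration". The SAP then explains why, once Treatment Period II begins, it needs a rule on which evaluation to use: "there is a possibility that the evaluation result of an adverse event may differ before and after the start of the study drug administration". The rule has two parts.

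- Period I analysis: "TEAEs that occur before the start of the study drug for Treatment Period II: The analysis will be performed based on the evaluation result" on the Period 1 AE page of the CRF.
- Analysis after the first SYR-472 tablet: both AE pages are used. Where they differ, the page for Period 2 and later "will be preferentially used". Time of onset counts the first SYR-472 tablet as day 1.

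**SAP 3.1.1 and 3.1.2.** Both analyses are tabulated by causality, intensity, seriousness and discontinuation, and the overview also lists "TEAEs leading to death". The after-SYR-472 analysis includes placebo subjects once they have switched, and the overview is also shown for the two groups combined. The onset categories in 3.1.2 begin at day 1.

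**Protocol 10.1.3.** Two neighbouring paragraphs govern recording. For an AE that worsens "after any change in study drug, the worsening or complication should be recorded as a new AE". For a change in intensity, "the event should be captured once with the maximum intensity recorded".

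**The concern.** The SAP plans for one AE record to span Week 12 with two evaluations. Because events are placed by onset date, the second evaluation has a place in the tables for one arm only. A placebo-onset AE lies outside the after-SYR-472 analysis, and the Period I analysis does not read the Period 2 page.

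AEs are the primary safety endpoint (Protocol 5.2.1), and long-term safety of SYR-472 is a stated objective (Protocol 5.1). The evaluations at risk are those that count most: severe, serious, leading to discontinuation, fatal. They would have arisen while the subject was taking SYR-472. Outputs could also disagree. The disposition table in SAP 1.1.5.2 could show a subject stopping study drug for an AE, with no matching entry among TEAEs leading to discontinuation.

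**Working it through.** The plan gives no figure on this point, so the check is a trace of one event through the rules in each arm, followed by a rough size.

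**Inputs**

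- Placement by onset date; two evaluation pages; Period 2 page preferred in the after-SYR-472 analysis only (SAP, definition of terms).
- First SYR-472 tablet: Week 0 in SYR-472/SYR-472, Week 12 in placebo/SYR-472 (Protocol 6.1).
- Recording of worsening (Protocol 10.1.3). The outcome table in Protocol 10.1.13 also allows an event to be closed because it was re-entered as another AE at higher intensity.

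**Trace.** An AE starts at Week 10 and has a worse evaluation at Week 20.

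| How Week 20 is recorded | SYR-472/SYR-472 | Placebo/SYR-472 |
|---|---|---|
| A. New AE, own onset date | New AE in the after-SYR-472 tables | New AE in the after-SYR-472 tables |
| B. Same record, re-evaluated on the Period 2 page | Period I table: Period 1 evaluation. After-SYR-472 tables: Period 2 evaluation | Period I table: Period 1 evaluation. After-SYR-472 tables: event absent. Period 2 evaluation used nowhere |

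Under A nothing is lost and the arms are treated alike. Under B the later evaluation is lost in the placebo/SYR-472 group only.

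**Does the protocol force route A?** Not reliably.

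1. The new-AE paragraph leads to A. The capture-once paragraph leads to B when the worsening is a rise in intensity. Neither says which prevails.
2. The protocol does not state that the Week 12 transition is a change in study drug in the sense of the first paragraph, although that is the natural reading.
3. Causality, action taken, outcome and seriousness are fields of an event record (Protocol 10.2.1.2). A change only in action taken, causality or outcome does not call for a new AE under either paragraph.
4. The SAP's own rule for one AE with two evaluations presupposes that some records follow route B.

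**Size.** The documents give no rates, so these are assumptions: about 50 subjects switch from placebo (53 per group are to be randomised); 30–60% have a Period I AE; 30–50% of those have one ongoing at Week 12; 5–15% of those receive a worse evaluation in Period II.

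- Low: 50 × 0.30 × 0.30 × 0.05 = 0.225, about 0.2 subjects.
- High: 50 × 0.60 × 0.50 × 0.15 = 2.25, about 2.3 subjects.

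These are counts before route A is allowed for. If a share *f* of the worse evaluations is entered as new AEs, both ends are multiplied by (1 − *f*). The share is unknown, but any value above zero lowers the range.

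One missed subject, using the 51 per group of Protocol 13.3 as denominator, is 1/51 = 2.0% of the placebo/SYR-472 group and 1/102 = 1.0% of the combined after-SYR-472 table.

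**The case against.** The best case on the other side is that the protocol already handles the clinically important events. Worsening or complication after a change in study drug is to be a new AE, and the outcome table in Protocol 10.1.13 foresees split records. A mild event that becomes serious on SYR-472 is ordinarily a worsening; so is one that becomes fatal. As a new AE it would have its onset after the first SYR-472 tablet and be counted in both arms. The capture-once paragraph speaks only of intensity and is arguably the more general of the two.

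That stands to a large extent. A reader might infer that every placebo-onset AE that becomes severe, serious, fatal or treatment-stopping on SYR-472 disappears from the tables. The documents do not support that: under the new-AE paragraph most such worsenings should be captured.

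A reader might also infer that sites cannot apply that paragraph because the Period I blind lasts to the end of the study (Protocol 8.4). That does not follow either. Protocol 8.1.1 defines separate study drugs for the two periods, and Protocol 8.2 has the investigator start the Period II drug after the Week 12 assessments. Every site can see the change of study drug without knowing the arm.

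The CRF pages and the Handling Rules for Analysis Data are not among the documents and might close the gap. However, the SAP states its evaluation rule in full in the definition of terms and does not refer to the Handling Rules there.

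What the objection does not remove is route B: sites that follow capture-once, and records where only action taken, causality or outcome changes.

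**Conclusion.** The point holds in conditional form. For a placebo-onset AE kept as one record, the SAP as written uses the Period 2 evaluation in no TEAE table, while it uses that evaluation for an identical record in the SYR-472/SYR-472 group. This follows from the text and needs no assumption about rates. The protocol reduces how often it happens but does not exclude it.

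The number of subjects is small and probably below the 0.2 to 2.3 range, which rests wholly on assumed rates and includes any worse evaluation. Serious, fatal or treatment-stopping cases would be fewer still. The point is nevertheless worth acting on: counts of such events in a group of about 50 may be very low, so a single case lost from one arm's tables for the primary safety endpoint is material. It has no bearing on the efficacy analysis.

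**What to change.** 1. **Protocol 10.1.3:** reconcile the two paragraphs so that it is explicit, for both arms, how worsening after the start of the Period II drug is recorded. If it is a new AE, it should have its own onset date.
2. **SAP 3.1.1 and 3.1.2:** add a separate table for placebo/SYR-472 subjects, listing AEs with onset before the first SYR-472 tablet whose Period 2 page shows higher intensity, new seriousness, drug withdrawn, fatal outcome or a changed causality. Use the Period 2 evaluation and present it alongside the after-SYR-472 tables. The Period I table keeps the Period 1 evaluation.

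Do not impute the onset of these events to SYR-472 day 1, which would distort the displays over time and by days since the last dose. Do not reclassify an event as emergent on SYR-472 because of a causality change alone; the TEAE definition rests on onset, and a separate table leaves it intact.

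Cost: a wording alignment in the protocol, one extra table and minor programming. The on-SYR-472 safety picture may look slightly less favourable.

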9.3.4 Week 52 in the Treatment Period or Early Termination

All procedures scheduled for the final visit will be performed at Week 52 of the treatment period.

For subjects prematurely withdrawn from the study during the treatment period, all procedures scheduled for Week 52 will be performed within 7 days after the final dose of the study drug (reckoned from the day after the final dose) whenever possible.

For all subjects receiving study drug, the investigator or sub-investigator must complete the End of Study eCRF page.

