The evaluable data within the acceptable window will be used. If more than one evaluable datum lies within the same acceptable window, the data whose test/observation/evaluation date is closest to the scheduled date will be used and, if there are two data equidistant to the scheduled date, the data obtained earlier will be used for efficacy endpoints and the data obtained later will be used for safety endpoints.

HbA1c

Visit	Scheduled Study Day	Acceptable Window			
		Study Day	Follow-up Day for Treatment Period I	Study Day for Treatment Period II	Follow-up Day for SYR-472 25 mg Tablet
Week -6	Study Day: -42	-49 to -29			
Week -2	Study Day: -14	-28 to -8			
Week 0	Study Day: 1	-7 to 1			
Week 2	Study Day: 15	2 to 22	~ 20	~ 1	
Week 4	Study Day: 29	23 to 42	~ 20	~ 1	
Week 8	Study Day: 57	43 to 70	~ 20	~ 1	
Week 12	Study Day: 85	71 to 98	~ 20	~ 1	
Week 16	Study Day: 113	99 to 126		2 ~	~ 20
Week 20	Study Day: 141	127 to 154		2 ~	~ 20
Week 24	Study Day: 169	155 to 182		2 ~	~ 20
Week 28	Study Day: 197	183 to 210		2 ~	~ 20
Week 32	Study Day: 225	211 to 238		2 ~	~ 20
Week 36	Study Day: 253	239 to 266		2 ~	~ 20
Week 40	Study Day: 281	267 to 294		2 ~	~ 20
Week 44	Study Day: 309	295 to 322		2 ~	~ 20
Week 48	Study Day: 337	323 to 350		2 ~	~ 20
Week 52	Study Day: 365	351 to 378		2 ~	~ 20
At the End of Treatment Period I	Follow-up Day for Treatment Period I: 7	2 ~	~ 20	~ 1	
At the End of Treatment Period II	Follow-up Day for SYR-472 25 mg Tablet: 7			2 ~ *	~ 20

*: At the end of Treatment Period II, "Study Day for Treatment Period II" will be assumed to be "Study Day for SYR-472 25 mg tablet."

Fasting blood glucose

Visit	Scheduled Study Day	Acceptable Window			
		Study Day	Follow-up Day for Treatment Period I	Study Day for Treatment Period II	Follow-up Day for SYR-472 25 mg Tablet
Week -6	Study Day: -42	-49 to -22			
Week 0	Study Day: 1	-21 to 1			
Week 2	Study Day: 15	2 to 22	~ 20	~ 1	
Week 4	Study Day: 29	23 to 42	~ 20	~ 1	

Visit	Scheduled Study Day	Acceptable Window			
		Study Day	Follow-up Day for Treatment Period I	Study Day for Treatment Period II	Follow-up Day for SYR-472 25 mg Tablet
Week 8	Study Day: 57	43 to 70	~ 20	~ 1	
Week 12	Study Day: 85	71 to 98	~ 20	~ 1	
Week 16	Study Day: 113	99 to 126		2 ~	~ 20
Week 20	Study Day: 141	127 to 154		2 ~	~ 20
Week 24	Study Day: 169	155 to 182		2 ~	~ 20
Week 28	Study Day: 197	183 to 210		2 ~	~ 20
Week 32	Study Day: 225	211 to 238		2 ~	~ 20
Week 36	Study Day: 253	239 to 266		2 ~	~ 20

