Week 44	Study Day: 309	295 to 322		2 ~	~ 20
Week 48	Study Day: 337	323 to 350		2 ~	~ 20
Week 52	Study Day: 365	351 to 378		2 ~	~ 20
Week 54	Follow-up Day for SYR-472 25 mg Tablet: 21				21 to 28
At the End of Treatment Period I	Follow-up Day for Treatment Period I: 7	2 ~	~ 20	~ 1	
At the End of Treatment Period II	Follow-up Day for SYR-472 25 mg Tablet: 7			2 ~ *	~ 20

*: At the end of Treatment Period II, "Study Day for Treatment Period II" will be assumed to be "Study Day for SYR-472 25 mg tablet."

Vital signs, laboratory test, creatinine clearance, eGFR

Visit	Scheduled Study Day	Acceptable Window			
		Study Day	Follow-up Day for Treatment Period I	Study Day for Treatment Period II	Follow-up Day for SYR-472 25 mg Tablet
Week -6	Study Day: -42	-49 to -29			
Week -2	Study Day: -14	-28 to -8			
Week 0	Study Day: 1	-7 to 1			
Week 2	Study Day: 15	2 to 22	~ 20	~ 1	
Week 4	Study Day: 29	23 to 42	~ 20	~ 1	
Week 8	Study Day: 57	43 to 70	~ 20	~ 1	
Week 12	Study Day: 85	71 to 98	~ 20	~ 1	

Visit	Scheduled Study Day	Acceptable Window			
		Study Day	Follow-up Day for Treatment Period I	Study Day for Treatment Period II	Follow-up Day for SYR-472 25 mg Tablet
Week 16	Study Day: 113	99 to 126		2 ~	~ 20
Week 20	Study Day: 141	127 to 154		2 ~	~ 20
Week 24	Study Day: 169	155 to 182		2 ~	~ 20
Week 28	Study Day: 197	183 to 210		2 ~	~ 20
Week 32	Study Day: 225	211 to 238		2 ~	~ 20
Week 36	Study Day: 253	239 to 266		2 ~	~ 20
Week 40	Study Day: 281	267 to 294		2 ~	~ 20
Week 44	Study Day: 309	295 to 322		2 ~	~ 20
Week 48	Study Day: 337	323 to 350		2 ~	~ 20
Week 52	Study Day: 365	351 to 378		2 ~	~ 20
Week 54	Follow-up Day for SYR-472 25 mg Tablet: 21				21 to 28

12-lead ECG

Visit	Scheduled Study Day	Acceptable Window			
		Study Day	Follow-up Day for Treatment Period I	Study Day for Treatment Period II	Follow-up Day for SYR-472 25 mg Tablet
Week -6	Study Day: -42	-49 to -22			
Week 0	Study Day: 1	-21 to 1			
Week 4	Study Day: 29	2 to 56	~ 20	~ 1	
Week 12	Study Day: 85	57 to 98	~ 20	~ 1	
Week 24	Study Day: 169	99 to 210		2 ~	~ 20
Week 36	Study Day: 253	211 to 308		2 ~	~ 20
Week 52	Study Day: 365	309 to 378		2 ~	~ 20
Week 54	Follow-up Day for SYR-472 25 mg Tablet: 21				21 to 28

Plasma concentration of SYR-472Z

Visit	Scheduled Study Day	Acceptable Window			
		Study Day	Follow-up Day for Treatment Period I	Study Day for Treatment Period II	Follow-up Day for SYR-472 25 mg Tablet
Week 4	Study Day: 29	23 to 42	~ 20	~ 1	
Week 12	Study Day: 85	71 to 98	~ 20	~ 1	

OTHER HANDLING

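### Safety visit windows leave a gap between the first open-label dose and Study Day 99, so early-termination values after one or two open-label doses miss the by-visit tables

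*SAP*

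**What the plan says.** The SAP section on handling of time windows covers every test, observation and evaluation item and says that "The evaluable data within the acceptable window will be used". Two clocks operate at the switch to open-label drug: Study Day, and a Period II clock for which "the day of the start of the study drug administration for Treatment Period II will be defined as Day 1 for Treatment Period II". Protocol 8.2 starts open-label drug after the Week 12 assessments.

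Rows of the safety window tables (columns: scheduled day, Study Day, Period I follow-up day, Period II day, SYR-472 follow-up day):

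- Vital signs, laboratory tests, creatinine clearance (Ccr) and eGFR: "Week 12 Study Day: 85 71 to 98 ~ 20 ~ 1", then "Week 16 Study Day: 113 99 to 126 2 ~ ~ 20".
- 12-lead ECG: "Week 12 Study Day: 85 57 to 98 ~ 20 ~ 1", then "Week 24 Study Day: 169 99 to 210 2 ~ ~ 20".

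The efficacy and weight tables also carry end-of-period rows, such as "At the End of Treatment Period II Follow-up Day for SYR-472 25 mg Tablet: 7". The two safety tables do not.

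For subjects withdrawn during treatment, Protocol 9.3.4 says that "all procedures scheduled for Week 52 will be performed within 7 days after the final dose of the study drug", whenever possible. Protocol 9.3.5 places the follow-up visit on the 21st day after the last dose. SAP 3.3.1.1, 3.3.2.1 and 3.3.2.2 list the safety visits as scheduled weeks only, whereas the compliance summaries in SAP 1.3.2 and 1.3.3 include a Week 52 or discontinuation visit.

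**The concern.** Week 12 requires that Period II Day 1 has not passed, and the next row requires Study Day 99 or later. A value taken after the first open-label dose but before Day 99 satisfies neither. The subjects most likely to have such a value are those who stop soon after the switch, because that is when their early-termination visit is due.

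For a subject in the placebo/SYR-472 group who stops after one open-label dose, that visit is normally the only assessment on SYR-472. The Week 12 assessment precedes the dose, the next scheduled visit is Week 16, and the 21-day follow-up was timed by reference to 5 half-lives (18.4 and 22.5 days, Protocol 6.2), so it is close to a washout assessment. Laboratory values, vital signs and ECG are the secondary safety endpoints. A value without a visit enters no by-visit summary and, for laboratory tests and ECG findings, no shift table.

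**Working it through.** **Assumption.** The columns in a row are read as joint conditions. Otherwise the Period II limits would have no effect.

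**The plan's own boundaries.** Scheduled day = 7 × week + 1, so Week 12 = 85 and Week 16 = 113. Laboratory and vital-sign windows from Week 12 on are scheduled day −14 to +13: 85 − 14 = 71 and 85 + 13 = 98; 113 − 14 = 99 and 113 + 13 = 126. These match the SAP.

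**The gap.** Let S be the Study Day of the first open-label dose. For day d on or after S, Period II day = d − S + 1. Week 12 needs d ≤ 98 and Period II day ≤ 1, so d ≤ S. The next row needs d ≥ 99 and Period II day ≥ 2. Days S + 1 to 98 therefore meet neither row:

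| Switch day S | Unassigned days | Count |
|---|---|---|
| 78 | 79–98 | 20 |
| 85 (nominal) | 86–98 | 13 |
| 92 | 93–98 | 6 |
| 98 | none | 0 |

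The result is the same for ECG, since its Week 12 row also closes on Day 98 and its Week 24 row also opens on Day 99.

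**No other row covers these days.** Week 54 needs SYR-472 follow-up day 21 to 28. After a single dose on Day 85 the earliest such day is 85 + 21 = 106. Week 52 needs Study Day 351 to 378 (laboratory and vital signs) or 309 to 378 (ECG), so performing the Week 52 procedures at early termination does not place the result there.

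**Early termination with S = 85.** After k open-label doses the last dose is on Day 85 + 7(k − 1), and the visit is due over the next 7 days:

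| Open-label doses | Last dose | Visit due | Unassigned |
|---|---|---|---|
| 1 | 85 | 86–92 | 7 of 7 |
| 2 | 92 | 93–99 | 6 of 7 (93–98) |
| 3 | 99 | 100–106 | 0 of 7 |

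**Late Week 12 visit.** If the switch falls after Day 98, a pre-dose value from Day 99 on is unassigned (S = 102: Days 99–102). Two limits are involved. The twelfth weekly Period I dose falls on 1 + 7 × 11 = Day 78, so the Period I follow-up limit of 20 is reached on 78 + 20 = Day 98. Without later Period I doses, a Day 99 value fails that limit as well as the Study Day limit.

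**Other outputs.** Markedly-abnormal-value (MAV) counts for laboratory tests and ECG are defined by period, not visit (SAP 3.3.1.1, 3.3.2.2). Vital signs have no MAV count (SAP 3.3.2.1); Ccr and high-sensitivity CRP have neither an MAV count nor a shift table. eGFR shares the window table, but SAP 3.3.1.1 plans no post-baseline eGFR summary, so nothing is lost there.

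**The case against.** A reader might infer that the placebo group's first SYR-472 exposure is excluded from the safety analysis, or that first-exposure data are kept in one arm and discarded in the other. The documents do not support either reading.

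- No scheduled visit falls in the gap. Subjects who continue contribute from Week 16 (ECG: Week 24), and their scheduled value would be chosen over an unscheduled one in the gap anyway.
- The gap applies equally to both arms. The first days of SYR-472 in the SYR-472/SYR-472 group do fall in a window (Week 2; Week 4 for ECG), but that contrast mainly reflects the protocol's visit schedule, with early visits in Period I and none for four weeks after the switch. No planned table is aligned on first exposure.
- Other analyses remain. Treatment-emergent adverse events have no visit windows, and clinically significant laboratory or ECG changes are recorded as adverse events (Protocol 10.1.3). The 21-day follow-up enters as Week 54. Period-based MAV counts and case plots are also planned.

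All of this stands, and it confines the point to subjects who stop after one or two open-label doses. It does not remove the point. The general window rule, read literally, could also restrict the MAV counts and case plots. The SAP does not say, and the supplied text includes neither its Appendix 2 nor the Handling Rules for Analysis Data. For vital signs, Ccr and high-sensitivity CRP there is no MAV count to fall back on.

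**Conclusion.** The gap holds, and it is minor. Under the joint reading, values after the first open-label dose and before Study Day 99 have no visit in either safety table: 13 days with the nominal Day 85 switch, more with an earlier switch, fewer with a later one. The established consequence is that early-termination values after the first or second open-label dose, in either arm, are missing from the by-visit summaries and the laboratory and ECG shift tables. Their loss from every safety output is not established.

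The affected outputs are descriptive, and the primary efficacy analysis is untouched. The number of subjects is not given and is probably small. Switch days other than 85 are illustrations, since the visit schedule in Protocol Appendix A is not in the supplied text. The late-Week-12 case is a lesser side issue.

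**What to change.** Make one of these changes to both safety window tables:

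1. Add the end-of-Treatment-Period-I and -II rows already used for efficacy and weight, and add them to the visit lists in SAP 3.3.1.1, 3.3.2.1 and 3.3.2.2. The Period II row takes SYR-472 day 2 or later and follow-up day up to 20, so unassigned early-termination days after the switch fall to 0.
2. Open the first Period II window (Week 16; Week 24 for ECG) at Period II Day 2 instead of Study Day 99. The closest-to-schedule rule still selects the scheduled visit where there is one.

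In either case, state that MAV counts and case plots use all evaluable values in the period.

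The cost is a small SAP edit and some loose labels. Under option 2 a Day 86 laboratory value labelled Week 16 lies 113 − 86 = 27 days before schedule. A Day 86 ECG labelled Week 24 lies 169 − 86 = 83 days before, against 169 − 99 = 70 already allowed. Under option 1, the footnote that counts from the first SYR-472 tablet would also give SYR-472/SYR-472 subjects who stop in Period I an end-of-Period-II value, so its wording needs a check when copied.

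For a late Week 12 visit, moving the Study Day 98 limit alone is not enough. When the last Period I dose was on Day 78, the Period I follow-up limit of 20 days must be extended with it. Otherwise leave that case as it is.
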